Main in- and exclusion criteria	
Main inclusion criteria:
 
• Patients with a confirmed diagnosis of advanced, unresectable and/or metastatic solid tumours, who have failed standard treatment, or for whom no therapy of proven efficacy exists, or who are not amenable to standard therapies• Eastern Cooperative Oncology Group (ECOG) performance status: 0 to 1• Presence of at least one measurable lesion according to response evaluation criteria in solid tumours (RECIST) 1.1 
Main exclusion criteria:
 
• Presence of active invasive cancers other than the one treated in this trial within 5 years prior to screening• HIV, HBV, or HCV infection• Inadequate organ function or bone marrow reserve as demonstrated by laboratory values• Active, known or suspected autoimmune disease• History (including current) of interstitial lung disease or pneumonitis within 5 years• Serious concomitant disease or medical condition affecting compliance with trial requirements• Patients with brain metastases• Patients receiving systemic treatment with any immunosuppressive medication within 1 week prior to treatment start

Proprietary confidential information © 2021 Boehringer Ingelheim International GmbH or one or more of its affiliated companies

Test product(s)	BI 891065 BI 754091 (Part B only)
dose	Part A: BI 891065: starting dose 100 mg once daily Part B: BI 891065: starting dose 200 mg per day BI 754091: fixed dose of 240 mg every three weeks
mode of administration	BI 891065: p.o. BI 754091: i.v. infusion
Comparator product(s)	Not applicable
dose	Not applicable
mode of administration	Not applicable
Duration of treatment	Administration will continue until progressive disease (PD), unacceptable toxicity, or other withdrawal criteria.
Statistical methods	In Parts A and B, dose escalation is guided by Bayesian Logistic Regression Models (BLRMs) with overdose control that will be fitted to binary toxicity outcomes. The estimate of parameters will be updated as data are accumulated using the BLRMs. At the end of the dose escalation, the toxicity probability at each dose level will be calculated to determine an estimate of the MTD and/or the RD. Descriptive analysis (summary statistics) will be used to describe the safety and efficacy endpoints.

Clinical Trial Protocol

Proprietary confidential information © 2021 Boehringer Ingelheim International GmbH or one or more of its affiliated companies

FLOW CHART

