2. TRIAL OBJECTIVES AND ENDPOINTS

2.1 MAIN OBJECTIVES, PRIMARY AND SECONDARY ENDPOINTS

2.1.1 Main objectives

The primary objective of this trial is:

Part A

- To determine the Maximum tolerated dose (MTD) and/or the recommended dose (RD) of BI 891065 monotherapy for further development in Asian patients with advanced solid tumours

Part B

- To determine the MTD and/or the RD of BI 891065 in combination with a fixed dose of BI 754091 at 240 mg for further development in Asian patients with advanced solid tumours

The definition of MTD and RD are as follows:

- MTD: the highest dose with less than 25% risk of the true DLT rate being equal or above 33% during the MTD evaluation period
- RD: RD is determined by SMC and it may be any dose which fulfil the escalation with overdose control (EWOC) criterion. The SMC may decide to declare a dose as RD without determining the MTD, in consideration of all available data including that from preceding trials.

The MTD will be determined based on the frequency of patients experiencing DLTs during the MTD evaluation period. The MTD evaluation period is defined as first treatment cycle (21 days). At the end of the dose escalation, the BLRM will be rerun using DLTs from all treatment cycles. This result as well as all available data will be used to define the RD.

The secondary objectives are:

Part A

- To document the safety and tolerability, and characterise pharmacokinetics (PK) of BI 891065 as monotherapy in Asian patients with advanced solid tumours

Part B

- To document the safety and tolerability, and characterise PK of the combination therapy of BI 891065 and BI 754091 in Asian patients with advanced solid tumours

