- Grade 3 tumour flare syndrome
- Grade 2 pneumonitis of any duration
- Grade 2 related uveitis, eye pain, or blurred vision that does not respond to topical therapy and does not improve to Grade 1 severity within 2 weeks or requires systemic treatment
- Treatment pause of BI 891065 for \geq 7 days in Cycle 1 due to treatment-related AEs
- Any treatment-related \geq Grade 2 toxicity that persists and results in a more than 2 weeks delay of administration of BI 754091 on Cycle 2 Day 1
- Any AEs that require dose reduction will be assessed by SMC and may be considered as DLTs unless the SMC considers the dose reduction as not strictly medically warranted
- Permanent treatment discontinuation according to section [4.1.6](#)

The frequency, time to onset, and severity of toxicities, as well as the success of standard medical management and dosing interruptions/delays, will be analysed to determine if a given toxicity should be considered a DLT for dose escalation purposes.

Late DLTs are AEs that meet the same grading criteria as DLT criteria but occur after the first cycle of study treatment. In order to assess the recommended dose, the BLRM will be rerun using all DLTs up until 90 days after the first administration of the last patient.

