7.5 RANDOMISATION

No randomisation will be performed. Patients will be assigned to escalating dose groups by order of admission into the trial.

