6. GENERAL ANALYSIS DEFINITIONS

6.1 TREATMENT(S)

In Part A of this Phase I trial, treatments are not randomized. Different dose levels and dose schedule of BI 891065 monotherapy are being administered.

The data will be presented only for Part A, because Part B was cancelled, as mentioned earlier.

For safety summaries events that start from the first administration of any trial medication until 30 days (REP) after the last administration of any trial medication will be considered as having occurred “on-treatment”. If not specified otherwise, all safety tables will be based on the on-treatment period. Adverse events that have onset during the screening or the follow-up period will be displayed in separate listings from those that occurred during the on-treatment period. The MTD evaluation period will be defined as the period from 1st treatment administration (day 1) till day 21 inclusively.

Labels of each treatment period, the labels used for displays in the tables and listings in the CTR, as well codes, decodes, sort order and labels for each trial medication are provided in the TSAP technical documents.

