7.4 PRIMARY ENDPOINT(S)

7.4.1 Primary analysis of the primary endpoint(s)

The primary endpoints of Part A are the MTD of BI 891065 and the number of patients with DLTs in the first treatment cycle. The number of patients with DLTs at each dose level will be presented for the first cycle for the MTD evaluation set and for the whole on-treatment period for the treated set separately.

The MTD will be determined by the SMC using recommendations from a Bayesian logistic regression model (BLRM, see CTP Section 7 for details on the model and on the prior). BLM evaluations for the CTR will be performed once using the number of patients with DLTs during the first cycle from the MTD evaluation set and once using the number of patients with DLTs during the whole on-treatment period from the treated set.

Tables and bar charts displaying the posterior probabilities of the true DLT rates being in either the underdosing interval, the targeted toxicity interval or the over toxicity interval will be produced.

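### The all-cycle BLRM rerun that informs the RD has two conflicting observation windows, and the protocol's calendar cut-off gives earlier cohorts longer potential follow-up that the model ignores

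*Protocol*

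**What the plan says.** Protocol 2.1.1 makes the RD part of the primary objective and adds a second model run to inform it: "At the end of the dose escalation, the BLRM will be rerun using DLTs from all treatment cycles". The result is used together with all available data.

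The documents describe the window of that run differently.

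- Protocol 4.1.7: "the BLRM will be rerun using all DLTs up until 90 days after the first administration of the last patient". This is a single calendar date for the whole trial.
- SAP 7.4.1 plans two runs for the trial report. One uses first-cycle DLTs in the MTD evaluation set. The other is run "once using the number of patients with DLTs during the whole on-treatment period from the treated set".
- SAP 6.1 defines on-treatment by "events that start from the first administration of any trial medication until 30 days (REP) after the last administration of any trial medication". Treatment is open-ended (protocol synopsis): "Administration will continue until progressive disease (PD), unacceptable toxicity, or other withdrawal criteria".
- SAP section 4 lists no departure from the protocol analyses.

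On dose order, protocol 7.5 states: "Patients will be assigned to escalating dose groups by order of admission into the trial". Protocol 7.1.1 defines the model parameter as the DLT probability in the MTD evaluation period, which 2.1.1 sets at 21 days. The likelihood has no exposure or time term.

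**The concern.** In the cycle 1 analysis every evaluable patient has the same 21-day window, so the yes/no outcome means the same thing at each dose. The all-cycle rerun gives that up. With a calendar cut-off, a patient in the first cohort can contribute a DLT at a time that the last patient has not yet reached. When escalation runs straight upward, longer observation goes with lower dose. A late DLT at a low dose then enters the likelihood exactly like a cycle 1 DLT. Because the curve is fitted jointly, it also moves the estimate at the highest dose.

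Separately, the same trial data can give two different answers depending on which document is followed. The RD may be any dose that meets EWOC, so the window could affect which doses appear eligible in this run.

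**Working it through.** **Inputs from the documents.** Part A prior (Table 7.1.1: 2): 0.9 weight on means (-3.66, -0.28), SDs (1.20, 0.83), correlation -0.10; 0.1 weight on means (-3, 0), SDs (2, 1), correlation 0. Reference dose 200 mg. EWOC: P(DLT rate ≥ 0.33) < 0.25. Cohorts of 3, 3 and 6 at 100, 200 and 400 mg, as in scenarios 8 to 12 of Table 10.4.1: 1.

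**1. Reproducing the plan's figures.** Grid integration of logit(π) = log α + β log(d/200) gives, for scenario 9 (0/3, 0/3, 1/6) at 400 mg, under/target/over probabilities of 0.820/0.157/0.023. The table has 0.814/0.163/0.023. All 12 scenarios agree within about 0.012.

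**2. Potential follow-up under protocol 4.1.7.** Let g be the days between cohort starts, with the last patient starting with the 400 mg cohort. Follow-up at 100/200/400 mg is (90 + 2g)/(90 + g)/90 days. Section 3.1 requires each cohort patient to have a DLT or complete 21 days before the model is updated, so g is about 21 or more.

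- g = 21: 132/111/90
- g = 42: 174/132/90
- g = 90: 270/180/90

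**3. What one extra late DLT does to the fit.** Adding one at 100 mg to scenario 9 (giving 1/3, 0/3, 1/6) raises the mean risk at 100 mg from 0.027 to 0.065. P(overdose) at 400 mg goes from 0.023 to 0.043, and the 400:100 mg risk ratio falls from 3.7 to 2.2. Adding one at 200 mg changes P(overdose) at 400 mg as follows:

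| Before | After | P(overdose), 400 mg | EWOC |
|---|---|---|---|
| 0/3, 0/3, 1/6 | 0/3, 1/3, 1/6 | 0.023 → 0.064 | still passes |
| 1/3, 0/3, 1/6 | 1/3, 1/3, 1/6 | 0.043 → 0.135 | still passes |
| 0/3, 0/3, 2/6 | 0/3, 1/3, 2/6 | 0.135 → 0.231 | still passes |
| 1/3, 0/3, 2/6 | 1/3, 1/3, 2/6 | 0.165 → 0.342 | now fails |

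**4. Long-run size.** The following are assumptions, not document figures: 21-day DLT rates p of 5/10/20%; constant hazard h = -ln(1 - p)/21 in cycle 1 and h/2 afterwards; exponential time on treatment with rate m = ln 2/median; no risk after stopping. The DLT probability seen by day T is

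h/(h+m) × [1 - e^(-21(h+m))] + e^(-21(h+m)) × (h/2)/(h/2+m) × [1 - e^(-(h/2+m)(T-21))].

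Example: 100 mg, median 168 days, so h = 0.00244 and m = 0.00413. T = 270 gives 0.048 + 0.146 = 0.194. T = 90 gives 0.048 + 0.061 = 0.109. Summing the posterior over all outcomes of 3 + 3 + 6 patients gives:

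| Gap / median (days) | Window | DLT % at 100/200/400 mg | Log-odds slope | 400 mg passes EWOC |
|---|---|---|---|---|
| 42 / 42 | calendar | 8.6/15.9/27.7 | 1.02 | 72.6% |
| | own 90 days | 7.5/14.6/27.7 | 1.12 | 73.6% |
| 42 / 84 | calendar | 12.5/21.5/34.4 | 0.94 | 55.3% |
| | own 90 days | 9.5/18.4/34.4 | 1.16 | 58.3% |
| 90 / 168 | calendar | 19.4/29.9/39.0 | 0.70 | 38.7% |
| | own 90 days | 10.9/21.0/39.0 | 1.19 | 47.7% |

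The differences in pass rate are 1.0, 3.0 and 9.0 points. With an equal true 21-day rate of 10% at every dose, 90-day gaps and a 168-day median, the calendar rule shows 34.8/29.9/21.0%: a falling curve with no dose effect.

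**5. The SAP window.** With complete follow-up and the same time on treatment at each dose, all cohorts are observed equally. Rates rise everywhere instead: 5/10/20% becomes 14.9/26.8/44.8% at an 84-day median. The two windows therefore do not estimate the same quantity.

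**The case against.** Several points count against a stronger claim, and most of them stand.

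- **Both windows confound dose with calendar time.** A reader might infer this, but the SAP window ends 30 days after each patient's own last dose, so cohort order does not set it. A data lock could cut it short, but protocol 11.4 reports only one patient still on treatment in April 2021, after the 29 March 2021 lock.
- **Early always means low dose.** Protocol 4.1.3 allows lower or intermediate doses later, so this holds only for uninterrupted escalation.
- **The low dose will look far worse.** Compounding an assumed monthly late hazard of 2% to 5% gives 1 - (1 - h)^9 = 17% to 37% against 1 - (1 - h)^3 = 6% to 14%. That keeps everyone at risk for nine months and ignores discontinuation, which the calculation above allows for.
- **One late DLT reverses the EWOC result.** It does so in the last row of the table in step 3, which already has three DLTs in 12 patients. In the other three rows 400 mg still passes.
- **The consequence is bounded.** The MTD uses cycle 1 DLTs only, the SMC weighs all safety data for the RD, and the shift at 400 mg is mostly in the cautious direction.
- **A 90-day limit has a price.** It removes genuine later DLTs from the model, so choosing it is a trade-off.

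None of this reconciles the two windows or supplies the missing time adjustment under the protocol wording. Long potential follow-up is also realistic here: the 100 mg cohort had reported by 14 February 2020 (Table 7.1.2: 1), 409 days before the lock. The dose of the patient still on treatment and the last patient's start date are not given.

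**Conclusion.** The point holds in a limited form. The protocol and the SAP give different windows for the all-cycle rerun, with no declared change. Under the protocol wording, earlier cohorts have longer potential follow-up, by a factor of 132/90 = 1.5 with 21-day gaps to 270/90 = 3.0 with 90-day gaps, and the binary model does not adjust for it. Late DLTs can then flatten the fitted curve and raise the estimated risk at 400 mg.

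Whether that matters depends on late DLTs occurring and on patients staying on treatment. The change in the chance that 400 mg passes EWOC ranges from about 1 point (6-week median, 42-day gaps) to about 9 points (24-week median, 90-day gaps), under the assumed rates and hazards in step 4. The documents do not support saying that the curve is distorted in every case, or that the MTD is affected. The rerun is one of several inputs to the RD, so this should be corrected but does not undermine the design.

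**What to change.** Reconcile protocol 2.1.1, protocol 4.1.7 and SAP 7.4.1 to one all-cycle rerun that counts DLTs with onset within 90 days of each patient's own first administration. This keeps the 90 days that the protocol already names, and the last patient can complete it.

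Alongside it:

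- Keep the whole on-treatment run as a labelled sensitivity analysis.
- Report follow-up time by dose level, since patients who stop early will still have less time on treatment.
- List DLTs after Day 90 with dose and day of onset for the SMC.

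The cost is a sentence in each of the three places, one date filter and a small table and listing. No new data are needed. The downside is that DLTs after Day 90 enter only the sensitivity run and the listing.

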4.1.8 Blinding and procedures for unblinding

Not applicable, as this is an open-label, single-arm trial.

4.1.9 Packaging, labelling, and re-supply

The investigational medicinal products will be provided by BI or a designated contract research organisation (CRO). They will be packaged and labelled in accordance with the principles of GMP. Re-supply to the sites will be managed via an IRT system, which will also monitor expiry dates of supplies available at the sites.

For details of packaging and the description of the label, refer to the ISF.

4.1.10 Storage conditions

Drug supplies will be kept in their original packaging and in a secure limited access storage area according to the recommended storage conditions on the medication label. A temperature log must be maintained for documentation.

If the storage conditions are found to be outside the specified range, the Clinical Research Associate (CRA) must be contacted immediately.

4.1.11 Drug accountability

The investigator or designee will receive the investigational drugs delivered by the sponsor when the following requirements are fulfilled:

- Approval of the CTP by the Institutional Review Board (IRB) / Independent Ethics Committee (IEC),
- Availability of a signed and dated clinical trial contract between the sponsor and the investigational site,
- Approval/notification of the regulatory authority, e.g. competent authority (CA),
- Availability of the curriculum vitae of the Principal Investigator,
- Availability of a signed and dated CTP,

Investigational drugs are not allowed to be used outside the context of this protocol. They must not be forwarded to other investigators or clinics. Patients should be instructed to return unused investigational drug.

The investigator or designee must maintain records of the product's delivery to the trial site, the inventory at the site, the use by each patient, and the return to the sponsor or warehouse / drug distribution centre or alternative disposal of unused products. If applicable, the sponsor or warehouse / drug distribution centre will maintain records of the disposal.

These records will include dates, quantities, batch / serial numbers, expiry ('use- by') dates, and the unique code numbers assigned to the investigational medicinal product and trial patients. The investigator or designee will maintain records that document adequately that the patients were provided the doses specified by the CTP and reconcile all investigational medicinal products received from the sponsor. At the time of return to the sponsor, the investigator or designee must verify that all unused or partially used drug supplies have been returned by the clinical trial patient and that no remaining supplies are in the investigator's possession.

4.2 OTHER TREATMENTS, EMERGENCY PROCEDURES, RESTRICTIONS

4.2.1 Other treatments and emergency procedures

There are no other mandatory treatments to be used in this trial or special emergency procedures to be followed. Recommendations for the management of immune-related AEs can be found in section [10.2](#).

Rescue medications to reverse the actions of BI 891065 or BI 754091 are not available. Therefore, potential side effects of BI 891065 or BI 754091 have to be treated symptomatically (relevant information is available in section [5.2.6.1.4](#)).

Concomitant therapy, with reasons for the treatment, must be recorded in the CRF during the screening and treatment periods, starting at the date of signature of informed consent and ending after the residual effect period (REP). After REP, only concomitant therapy indicated for treatment of a related AE has to be reported. If a new anti-cancer treatment is started, it will be documented in the CRF, on a separate page of follow-up therapy, different from the concomitant therapies pages.

4.2.1.1 Permitted concomitant medications

- If medically feasible, patients taking regular medication should be maintained on it throughout the trial.
- Pre-medication is not required, but may be utilised following the first dose of study medication. This includes medications for the management of nausea, diarrhoea, and vomiting for which the patient must be treated according to institutional standards.
- Supportive care and other medications that are considered necessary for the patient's well-being may be given at the discretion of the Investigator.
- Blood transfusions are allowed at any time during the trial, except to meet inclusion criteria. There must be at least 4 weeks between a patient's last transfusion and the screening laboratory assessment. Exceptions to this will be considered by the Sponsor on a case-by-case basis.

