3.3.4.1 Discontinuation of trial treatment

An individual patient will discontinue trial treatment if:

- The patient wants to discontinue trial treatment, without the need to justify the decision.
- The patient has repeatedly shown to be non-compliant with important trial procedures and, in the opinion of both, the investigator and sponsor representative, is not willing or able to adhere to the trial requirements in the future.
- The patient needs to take concomitant medication that interferes with the investigational medicinal product or trial assessments. Refer to section [4.2.2.1](#) for prohibited concomitant medications.
- Progressive disease according to RECIST v1.1 and/or iRECIST. Refer to section [5.1.1](#) for details and exceptions.
- The patient can no longer receive trial treatment for medical reasons (such as surgery, other diseases, or pregnancy).
- The patient experiences an AE requiring treatment discontinuation as listed in section [4.1.6](#).

Even if the trial treatment is discontinued, the patient remains in the trial and will undergo the procedures for the end of treatment visit and follow-up visits as outlined in the [Flow Chart](#) and section [6.2.3](#).

For all patients the reason for withdrawal from trial treatment (e.g. AEs) must be recorded in the CRF. These data will be included in the trial database and reported.

Patients meeting the following criteria will be considered non-evaluable for DLT. If less than two patients are evaluable for DLT in a cohort, the non-evaluable patients will be replaced;

- Patient withdrawal for a reason other than DLT before completing the first treatment cycle
- Patients who have reduced BI 891065 dose level during the first treatment cycle, unless they develop a DLT

Proprietary confidential information © 2021 Boehringer Ingelheim International GmbH or one or more of its affiliated companies

- Patient who can't be assessed for safety due to missed visits in the first cycle of treatment and who does not experience DLTs
- Patient who misses >5 doses of BI 891065 during the first treatment cycle for reasons other than treatment-related AEs and who does not experience DLTs
- (Part B only) Patients who have received less than 50% of the BI 754091 initial dose, unless they develop a DLT

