4.2.2 Restrictions

4.2.2.1 Restrictions regarding concomitant treatment

- No other investigational therapy or anticancer agent should be given to patients. If such agents are required for a patient, then the patient must first be withdrawn from the trial.
- Immunosuppressive medications including, but not limited to systemic corticosteroids at doses exceeding 10 mg/day of prednisone or equivalent, methotrexate, azathioprine, and tumour necrosis factor-alpha blockers are prohibited. Use of immunosuppressive medications for the management of investigational product-related AEs or in patients with contrast allergies is acceptable, and does not necessarily warrant immediate treatment discontinuation. In addition, use of inhaled, topical, intranasal corticosteroids or local steroid injections (e.g., intra-articular injection) is permitted. Temporary uses of corticosteroids for concurrent illnesses (e.g., food allergies, computed tomography [CT] scan contrast hypersensitivity) are acceptable. For the treatment of CRS, supportive therapy including steroids and/or interleukin 6 receptor (IL6R) antagonists ([R15-0031](#)) may be used as clinically indicated.
- Pre-medications should not be given in cycle 1 to avoid masking the emergence of DLTs.
- Live attenuated vaccines are prohibited from informed consent until 30 days after the last dose of investigational product.
- Herbal preparations/medications are not allowed throughout the trial. These herbal medications include, but are not limited to: St. John's wort, kava, ephedra (ma huang), gingko biloba, dehydroepiandrosterone (DHEA), yohimbe, saw palmetto, and ginseng. Patients should stop using these herbal medications at least 7 days prior to first dose of study treatment.
- Patients already receiving erythropoietin at the time of screening for the trial may continue it, provided they have been receiving it for more than one month at the time trial treatment is started. Prophylactic erythropoietin should not be started during the first 3 weeks of treatment, but may be started thereafter. In Japan, no erythropoietin product is approved for anaemia associated with cancer chemotherapy.
- Prophylactic granulocyte colony stimulating factors are not allowed during the first 3 weeks of treatment.

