6.2 IMPORTANT PROTOCOL DEVIATIONS

Important protocol deviations will be summarised. The IQRMP specifies the important protocol deviations in detail. The following table specifies the different categories of IPDs.

Table 6.2: 1 Handling of iPDS

| iPD code | | iPD Category & Brief Description | Excluded from analysis set |
|-----------------|----|---|-----------------------------------|
| A | | In/Exclusion criteria not met | None |
| | A1 | Inclusion criteria not met | None |
| | A2 | Exclusion criteria not met | None |
| B | | Informed consent not available/not done | |
| | B1 | Informed consent not available/not done | All |
| | B2 | Informed consent too late | None |
| C | | Trial medication and randomization violations | |
| | C1 | Incorrect trial medication taken | None |
| | C2 | Administration not according to protocol | None |
| | C3 | Administration of study medication which exceeded the limit of in-use stability | None |
| D | | Prohibited medication use | |
| | D1 | Concomitant medication | None |
| E | | Missing critical data | |
| | E1 | Missing of Vital signs (BP, PR, BT and SpO2) | None |
| | E2 | Missing of 12-Lead ECG | None |
| | E3 | Missing of Safety laboratory parameters | None |
| | E4 | Important AE related data missing | None |

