7.2 CONCOMITANT DISEASES AND MEDICATION

Descriptive statistics are planned for this section of the report. Concomitant diseases will be coded similarly as adverse events based on the most current Medical Dictionary for Regulatory Activities (MedDRA) version. Concomitant therapies (CTs) will be coded according to World Health Organization Drug Dictionary (WHO DD). CTs will be classified according to the Anatomical Therapeutic Chemical (ATC) classification system. The third ATC level will be used to categorise CTs by therapy type. In situations where a medical product may be used for more than one equally important indications, there are often several classification alternatives. As appropriate, patients receiving CTs with more than one possible ATC level 3 categories will be counted more than once. Footnotes will clarify this possible double counting in tables.

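### Protocol 4.2.1.1 permits pre-medication from the first dose onward, inside the cycle 1 window in which 4.2.2.1 bars it to avoid masking DLTs; the permission is the half to correct

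*Protocol*

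**What the plan says.** Two current sections of the protocol address pre-medication.

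- **Section 4.2.1.1 (permitted medications):** "Pre-medication is not required, but may be utilised following the first dose of study medication". The next sentence says that this includes drugs for managing nausea, diarrhoea and vomiting. No cycle is excluded.
- **Section 4.2.2.1 (restrictions):** "Pre-medications should not be given in cycle 1 to avoid masking the emergence of DLTs".

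Section 2.1.1 makes the first 21-day cycle the MTD evaluation period, and section 4.1.7 uses only cycle 1 DLTs to determine the MTD. SAP 7.4.1 accordingly fits the model to "the number of patients with DLTs during the first cycle from the MTD evaluation set", with a second fit to DLTs over the whole on-treatment period.

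Three provisions bear on how such use would be seen. Protocol 4.2.1 requires that "Concomitant therapy, with reasons for the treatment, must be recorded in the CRF". SAP 7.2 says of concomitant therapies (CTs): "The third ATC level will be used to categorise CTs by therapy type". SAP Table 6.2: 1 has a category for prohibited medication use, with the row "D1 | Concomitant medication | None"; the last entry means that the deviation removes nobody from an analysis set.

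**The concern.** A site following 4.2.1.1 as written could give a prophylactic anti-emetic from the second dose of BI 891065 onward. That is what 4.2.2.1 warns against, because it could hide a DLT. The cycle 1 DLT count is a primary endpoint and the input to the Bayesian logistic regression model (BLRM) that guides dose choice. In cohorts of about three patients, one event that never appears can change the recommended step.

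Protocol 4.1.7 can deal with an event that occurs and is then treated: it exempts short, resolving Grade 3 nausea or vomiting and has the success of medical management considered. It cannot deal with an event that prophylaxis prevented.

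**Working it through.** **1. How far the two rules overlap.** Doses are counted from flow chart footnote o, over a 21-day cycle.

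| Schedule | BI 891065 doses in cycle 1 | Doses after the first, still in cycle 1 |
|---|---|---|
| Part A q.d. (day 2 skipped) | 21 - 1 = 20 | 20 - 1 = 19 |
| Part A b.i.d. (four doses skipped) | 42 - 4 = 38 | 38 - 1 = 37 |
| Part B q.d. (no exceptions) | 21 | 21 - 1 = 20 |
| Part B b.i.d. (two doses skipped) | 42 - 2 = 40 | 40 - 1 = 39 |

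For every dose in the last column, 4.2.1.1 allows pre-medication and 4.2.2.1 bars it. BI 754091 is infused on day 1 of each cycle, so its next scheduled dose falls in cycle 2 and the two rules could agree for that drug. SAP section 3 says that Part B was cancelled and that study medication means BI 891065 alone.

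**2. Which rule is the intended one.** Only 4.2.2.1 gives a reason, and the reason protects the primary endpoint. The same section bars starting prophylactic erythropoietin, and any prophylactic G-CSF, in the first 3 weeks. Keeping prophylaxis out of the DLT window is therefore a consistent intention, and the unrestricted permission is out of line with it.

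**3. Sensitivity of a small cohort.** Table 10.4.1: 1 in the protocol gives the model's next step after three patients at 100 mg. With 1/3 DLTs the step is 200 mg (400 mg capped by the 100% rule). With 2/3 it is 50 mg. Table 7.1.2: 1 reports 1/3 at 100 mg for this trial. This shows what one unseen event could do. It does not show that one was missed.

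**4. Illustrative size.** The documents give no input for this, so every component is assumed. Let m = (gastrointestinal share of DLTs) x (share of patients pre-medicated) x (share of events prevented).

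- Low: 0.10 x 0.25 x 0.50 = 0.0125
- High: 0.25 x 0.50 x 0.50 = 0.0625
- Extreme: 0.25 x 1 x 1 = 0.25

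On the q.d. grid of Table 10.4.1: 1, after no DLTs at 100 and 200 mg, 2/6 at 400 mg keeps 400 mg and 3/6 moves the recommendation to 200 mg. The chance of at least 3 DLTs in 6 is P(X >= 3), with X ~ Binomial(6, p(1 - m)).

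| True rate p at 400 mg | m = 0 | m = 0.0125 | m = 0.0625 | m = 0.25 |
|---|---|---|---|---|
| 0.33 (overdose boundary) | 31.3% | 30.5% | 27.3% | 16.5% |
| 0.107 (prior mean, Table 7.1.1: 3) | 1.9% | 1.8% | 1.6% | 0.9% |

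The 3/6 threshold would not carry over unchanged if 200 mg b.i.d., modelled as 300 mg q.d., were among the candidate doses.

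**The case against.** The strongest reply is that the two sections can be read together. A general, optional permission gives way to a specific, reasoned restriction, so a site reading both would withhold pre-medication in cycle 1. The sentence on nausea, diarrhoea and vomiting also speaks of management and treatment, which suggests symptoms already present. This has some force and keeps the point minor. It does not remove the conflict: the subject of the bullet is pre-medication, the next bullet already allows supportive care, and no text separates prophylaxis from treatment.

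Three stronger readings are tempting, and the documents do not support them.

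- **That such use would go unhandled.** Deviation category D is its natural home, and SAP 6.2 has important deviations summarised. Excluding no one from an analysis set is not the same as having no rule. The detailed deviation definitions sit in the IQRMP, which cannot be seen here.
- **That a supportive BLRM fit without pre-medicated patients is needed.** Protocol 3.3.4.1 makes patients non-evaluable for inadequate exposure or assessment, for example "Patients who have reduced BI 891065 dose level during the first treatment cycle, unless they develop a DLT". A fully dosed and fully observed patient is different. Dropping only patients without a DLT must push the toxicity estimate up, whether or not anything was masked, and cannot recover a masked event.
- **That only gastrointestinal drugs matter.** Section 4.2.1.1 gives these as an inclusion, not a limit, and 4.2.2.1 bars all pre-medication. Section 1.2.1 lists cytokine release syndrome, and no gastrointestinal event, among the class's higher-grade or dose-limiting events. Any check should cover every drug class.

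**Conclusion.** The contradiction stands in current text, and 4.2.1.1 is the half that is wrong as written. It matters because following it would do what 4.2.2.1 says could mask DLTs. Severity is minor.

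A reader might infer that the MTD was biased. The documents do not support that: they do not show that any patient was pre-medicated. The effect is unquantified and probably small. The illustrative fall from 31.3% to between 30.5% and 27.3% at a true rate of 0.33 rests wholly on assumed shares and covers gastrointestinal drugs only. The conclusion about the wording depends on none of these figures. It rests on the daily dosing schedule and on the reason that 4.2.2.1 gives.

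**What to change.** Amend Protocol 4.2.1.1 to read: 'Prophylactic pre-medication is not required and should not be given in cycle 1 (see 4.2.2.1); it may be used from cycle 2. Treatment of nausea, diarrhoea or vomiting that has occurred is allowed at any time.' This keeps the strength of the wording in 4.2.2.1.

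The rationale for Global Amendment 4 says that primary and secondary endpoint assessments are complete, so the edit mainly corrects the record. The useful step now is in reporting: list any prophylactic pre-medication of any class given in cycle 1 under deviation D1, identified from concomitant therapy and its recorded reason. If there was none, say so. Leave the planned BLRM analyses as they are.

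The cost is a short rewording of one bullet and one check of recorded data, with no new data collection and no extra model run.
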